4.4 Secondary Preliminary Effectiveness Outcomes (Stepped-Wedge Trial Only)

4.4.1 Stepped-Wedge Trial

Re-engagement in TB/HIV care. The rate of patient re-engagement at the CHW level and time to re-engagement in TB/HIV care at the patient level in the six months prior to the CHW training compared to six-months following the CHW training will be evaluated using chart extraction. We will apply a Poisson regression model to compare rates of patient re-engagement at the CHW level, accounting for both clinic random effect and the fixed effect of time in the stepped wedge design. Pre-intervention patient re-engagement rates will be collected during the TAU phase for each clinic over the six months prior to the first CHW training, and post-intervention rates will be collected six months after the CHW training is complete via chart review. A Wald test will be used to test the effect of the CHW training intervention on the rates of patient re-engagement.

Time to re-engagement. To further investigate whether the CHW training intervention decreases patient time to re-engagement in TB/HIV care over six months, we will use a Cox Proportional Hazard survival model to model the patient-level outcome of time of re-engagement. Right censoring (those who do not re-engage within six months) is handled in the Cox model. A frailty model includes the random effect of clinics to account for unobserved heterogeneity. If the proportional hazard assumption is not met, the parametric accelerated failure time model can be used instead. We will control for amount of CHW contact with the patient (i.e., whether the CHW makes contact with the patient and the number of times the CHW visits the patient before the patient re-engages) and the patient's screening results (i.e., whether they screen positive for depression, hazardous alcohol use, and/or other drug use).

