NGO leader and stakeholder perceptions of feasibility and acceptability: Following the 6MFU assessment timepoint and collection of mixed-methods feasibility and acceptability data from CHWs, we will conduct qualitative interviews with leadership staff from NGOs, as well as policymakers and other stakeholders. These interviews will explore their perceptions of the feasibility and acceptability of the stepped-wedge training and aid in interpretation of data from CHWs themselves. Further, understanding organizational and systems barriers and facilitators to this training has important implications for longer term sustainment.

Patient Re-Engagement.

Chart Extraction. Chart extraction will be used to examine the rate of patient re-engagement in TB/HIV care. Specifically, data will be extracted from a centralized database of routinely collected data (*the Western Cape Province's Health Data Center*), which is hosted within the Western Cape Department of Health. The database includes information pertaining to demographic information, TB and HIV status, including whether TB and/or HIV treatment was initiated, date of initial diagnosis, lost-to-follow-up for TB and/or HIV care (i.e., missed treatment for two consecutive months), and date of TB and/or HIV treatment visits. This data is available by site and by unique patient health identification number (PHIN).

Around the time of a group's training, trained study researchers will receive a list of PHINs assigned to each CHW in the group in the past six-months from CHW supervisors/ workers overseeing CHWs. Aggregating data by CHW, and only viewing patients' PHIN and TB/HIV attendance data, we will extract whether patients re-engage, the time to re-engagement among those who return to care, and where patient re-engage in the six-months before the training.

Approximately six-months after a group's training, trained study researchers will receive a list of PHINs assigned to each CHW in the group since the training. Aggregating data by CHW, and only viewing patients' PHIN and TB/HIV attendance data, we will extract whether patients re-engage, the time to re-engagement among those who return to care, and where patient re-engage in the six-months before the training.

As only aggregate, de-identified data will be extracted from a centralized database, patients will not need to give informed consent.

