4.3 Primary Preliminary Effectiveness Outcomes (Stepped-Wedge Trial Only)

4.3.1 –Stepped Wedge Trial

CHW Stigma. The primary measure of CHW stigma is the Social Distance Scale (SDS),^{20,43,44} a well-validated measure of stigma used to capture health-related stigma across conditions and has been recommended for assessing mental health stigma among healthcare providers. A total SDS score will be calculated to represent CHW stigma towards the target population at each timepoint, with high scores indicating greater desire for social distance. First, we will conduct descriptive analyses (e.g., mean, standard deviation) to summarize the CHW stigma, using the continuous SDS score. The data distribution will be assessed to see whether the underlying assumptions are met (e.g., normality). To account for the stepped wedge study design, we will fit a linear mixed model (LMM). This analytic approach will allow us to account for both random effects of the clinic and CHW, and fixed effects of time and the effect of the training. We will analyze the within- and between-group effects. Specifically, the within group effect will evaluate changes in stigma before and after receiving the training with CHWs from the same clinic,

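### The Cox and Poisson models for patient re-engagement allow for clinic but not CHW correlation: the Cox test mainly risks false positives, and the Poisson error could go either way

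*Combined protocol and SAP*

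**What the plan says.** Section 4.4.1 sets out two analyses.

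- **Rate:** "We will apply a Poisson regression model to compare rates of patient re-engagement at the CHW level". On the terms in that model, the section adds that it works by "accounting for both clinic random effect and the fixed effect of time in the stepped wedge design". For inference, "A Wald test will be used to test the effect of the CHW training intervention".
- **Time to re-engagement:** a patient-level Cox model, censored at six months. "A frailty model includes the random effect of clinics to account for unobserved heterogeneity". Covariates are also planned: "We will control for amount of CHW contact with the patient", plus the patient's screening results.

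The data structure is in section 3.5.2g. Researchers receive "a list of PHINs assigned to each CHW in the group in the past six-months", and later a second list for the period since training. Each CHW therefore contributes a set of patients to each window.

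The linear mixed model for the Social Distance Scale in section 4.3.1 is specified to "account for both random effects of the clinic and CHW, and fixed effects of time and the effect of the training". No section carries the CHW level over to the two re-engagement models, and none names a dispersion parameter or a robust variance for them.

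**The concern.** Patients seen by the same CHW may resemble one another, and a CHW's results may shift between windows for reasons other than training. A model that knows only the clinic treats patients of one CHW as no more alike than patients of different CHWs in that clinic. Its standard error for the training effect can then be wrong. The Poisson model has a second possible error: if each patient simply does or does not re-engage, the Poisson variance is larger than the true variance.

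These are secondary outcomes of a pilot, labelled preliminary. They are nevertheless the trial's only patient-level effectiveness outcomes, and section 5.3.2 links possible scale-up partly to re-engagement.

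**Working it through.** **Inputs from the documents.** 60 CHWs (section 3.3.2a); about 20 per cluster, hence about three clusters (3.2.2), although 4.1.1 mentions six clinics and 3.1.2 leaves the clinics open; training in months 5, 6 and 7 (section 7); six-month windows (4.4.1). The plan has no power or variance figure for re-engagement to reproduce.

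**Assumed, not in the documents.** Re-engagement probability p = 0.3 or 0.7; mean 18 or 36 patients per CHW per window; CHW standard deviations (SDs) of 0.3 or 0.5 on the logit or log-hazard scale, after covariates; caseloads equal, unequal but shared across windows, or drawn separately per window with coefficient of variation (CV) 0.4 or 0.8.

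**1. Poisson variance on a yes/no outcome.** With n patients assigned as denominator, the variance of the log rate is 1/(np) under Poisson and (1−p)/(np) under binomial. The model SE is too large by 1/√(1−p).
- p = 0.3: 1/√0.7 = 1.20. The nominal 5% test needs |Z| > 1.96 × 1.195 = 2.34, so it rejects about 1.9%.
- p = 0.7: 1/√0.3 = 1.83, needing |Z| > 3.58, about 0.03%.

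This does not come from omitting CHW. With a person-time denominator to first event, it does not arise.

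**2. Omitted CHW variation.** For the Cox contrast, model variance is about 2/D, with D events per window. Two sources are missed:
- CHW-by-period variation, SD τ: adds 2τ²/60.
- Stable CHW differences, SD σ, when caseloads are drawn separately with CV c: adds 2c²σ²/60. This is zero if each CHW's caseload share is the same in both windows.

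| Case | 2/D | Added | SE ratio | Rejection, by hand | Simulated range |
|---|---|---|---|---|---|
| τ = 0.3, 18 patients, p 0.3 (D = 324) | 0.00617 | 0.00300 | 0.82 | 10.8% | 10.9–27.2% |
| τ = 0.3, 36 patients, p 0.7 (D = 1512) | 0.00132 | 0.00300 | 0.55 | 27.8% | same range |
| σ = 0.5, c = 0.4, 18 patients, p 0.3 | 0.00617 | 0.00133 | 0.91 | 7.6% | 7.4–14.1% |
| σ = 0.5, c = 0.4, 36 patients, p 0.7 | 0.00132 | 0.00133 | 0.71 | 16.7% | same range |

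**3. Null simulation** (120 cells, 900 runs each; Monte Carlo SE about 0.7 points at 5%). Clinic strata stood in for the Cox frailty; contact and screening covariates were not simulated.
- *Cox, clinic only:* no CHW variation 3.6–6.6%; stable SD 0.5 with equal caseloads 3.0–4.9%, unequal but shared 4.7–6.2%, separate CV 0.8 14.8–32.7%; harshest cell 53.3%.
- *Poisson, pre/post totals, no calendar term:* no CHW variation 0–2.6%; stable SD 0.5 with separate caseloads CV 0.8, 0.2–10.1%; CHW-by-period SD 0.5, 1.6–23.6%. The ratio of model SE to true SE was below 0.95 in 34 cells and above 1.05 in 76.
- *Poisson, monthly counts with month effects:* 0–5.8%.
- *CHW-clustered robust variance with t reference:* Cox 3.7–7.8%, Poisson totals 3.8–7.6%, Poisson monthly 3.8–8.0%. Clinics were fixed effects or strata in these runs, so the combination with a clinic random effect was not itself simulated.
- *Cox stratified by CHW*, standing in for a CHW intercept or frailty alone: 9.1–54.4% under CHW-by-period variation.

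A second simulation over 5–20 patients and rates of 10–60% gave about 3–39% for clinic-only Cox, 0.1–22% for Poisson totals with counts bounded by caseload, and 4–8% with CHW-clustered variance.

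**4. Fixed clinics and calendar trend.** With the 3.5.2g windows and one pre and one post total per CHW, the gap between windows is the same in every clinic. A linear trend is then an exact combination of clinic and training: design rank 4 of 5 with three clinics, 7 of 8 with six. It is estimable with random clinics (3 of 3), with monthly counts (5 of 5), or with one common pre-window (5 of 5), as "over the six months prior to the first CHW training" can be read.

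**The case against.** **The Poisson false positives depend on a reading of the plan.** The inflated figures come from totals without a calendar term, whereas 4.4.1 plans a time effect. With month effects the range is 0–5.8%, which is mainly lost power. This stands, and it limits the Poisson part.

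**The denominator is not stated.** This stands; the over-large SE applies only if the denominator is patients assigned.

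**The large Cox figures are conditional.** With stable CHW differences and equal or shared caseloads, rejection is 3.0–6.2%. The planned contact and screening covariates could absorb some CHW variation. Both points stand, but nothing in the plan ensures those conditions.

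**A Wald test does not exclude a robust variance.** True: it is unspecified, not ruled out. But an analyst following 4.4.1 has no instruction to account for CHW.

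**The remedy can do worse.** With clinic-by-period SD 0.2 and three clinics, robust monthly Poisson rejects 12–15% against 2–11% as planned, and robust totals 22–41% against 17–41%. Robust Cox improves, 24–57% against 51–68%, but stays far from 5%. This stands as a limit to state.

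**Stronger readings to avoid.** A reader might infer that both tests are biased towards false positives; the Poisson direction cannot be told from the documents. A reader might also infer that copying the CHW random intercept from the primary model is enough; it does not cover CHW-by-period variation. Nor does this point touch the Social Distance Scale analysis, which includes the CHW effect.

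**Conclusion.** The point holds in limited form. As written, neither re-engagement model accounts for CHW-level correlation, and the plan's own data structure makes such correlation possible.

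- **Cox:** the test is sound under stable CHW differences and similar caseloads. Otherwise it mainly risks a false positive, about 7–25% at nominal 5% under moderate assumed variation.
- **Poisson:** the net error is of unknown direction. With month effects and no clinic-by-period variation, the test is mainly conservative.

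The sizes depend on assumed caseloads, rates and CHW variances. The outcomes are secondary and preliminary, so this is a cheap improvement that should be made, led by the Cox model; it is not a threat to the primary effectiveness result.

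**What to change.** Amend section 4.4.1 as follows.

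1. Keep both models with their planned clinic and time terms.
2. State the Poisson denominator (offset): patients assigned or person-time.
3. Base both tests on CHW-clustered robust variance with a small-sample t reference, for example CHWs minus clinics as degrees of freedom (60 − 3 = 57, or 60 − 6 = 54).
4. If the software cannot combine this with the clinic frailty, stratify the Cox model by clinic. Fixed clinic effects in the Poisson model are not required. If they are used, split counts by calendar month, or state that with one pre and one post total per CHW a linear trend is not separated from training.
5. State the limit: clinics are the randomised unit and are few, CHW-clustered variance does not cover clinic-by-period variation, and the robust Poisson test can then reject more often than the planned one. Report both results as preliminary.

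**Cost:** SAP wording, and keeping the CHW identifier already used for aggregation. No extra participants or visits. Only the optional monthly split needs patient assignment dates, which section 3.5.2g does not list and which must fit its commitment to aggregate, de-identified data; the Cox model needs a start date in any case.

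### Neither re-engagement model has a case-mix covariate documented as fixed at assignment, so a case-mix change that starts at each clinic's training can be read as a training effect

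*Combined protocol and SAP*

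**What the plan says.** Section 3.5.2g describes two extractions for each training group. Around the time of training, researchers "will receive a list of PHINs assigned to each CHW in the group in the past six-months". About six months after training, they "will receive a list of PHINs assigned to each CHW in the group since the training". The database holds demographics, TB and HIV status, treatment initiation, date of diagnosis and "date of TB and/or HIV treatment visits", but staff will view only the patient identifier and attendance data.

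Section 4.4.1 specifies two models:

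- **Rate of re-engagement, CHW level.** "We will apply a Poisson regression model to compare rates of patient re-engagement at the CHW level, accounting for both clinic random effect" and, in the same sentence, a fixed effect of time. It names no patient or CHW covariate and no offset.
- **Time to re-engagement, patient level.** A Cox model: "A frailty model includes the random effect of clinics to account for unobserved heterogeneity". For covariates the plan says "We will control for amount of CHW contact with the patient", which includes the number of visits before re-engagement, and adds screening results for depression, hazardous alcohol use and other drug use. It names no calendar-time term.

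The documents do not say when screening is done. Section 2.3 mentions it alongside the CHWs' visit documentation. By contrast, Section 4.3.1 does name covariates for the stigma model (CHW demographic and job characteristics).

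**The concern.** Only the timing of training is randomised, and it is randomised by cluster. Which patients a CHW is given in each window is not randomised. If the mix of easy and hard cases changes when a clinic is trained, the comparison of the two lists reflects that change as well as the training. A shift towards long-lost patients could hide a real benefit, and a shift away from them could make an ineffective training look useful.

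The planned covariates offer little protection. CHW contact and visit counts arise after assignment and may themselves change with training. Screening results describe case mix, but if CHWs screen at their visits, the results also follow assignment and could be affected by a training on depression and substance use. Re-engagement is the trial's patient-level effectiveness outcome, and Section 5.3.2 links it to scale-up.

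**Working it through.** **The plan's own figures.** The only power figures (86% at effect 0.63 and 96% at 0.75, Section 3.3.2a) are for the stigma score. The documents give no re-engagement rate, effect size or patient count, so there is no figure to reproduce, and the sizes below rest on assumptions.

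**Step 1. What the fixed time effect can remove.** Take three clinics trained in months 5, 6 and 7 (Section 7), with six months of assignments before and six after each clinic's own training. Assume time is coded as calendar month and work on the log-rate scale with equal weights.

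- Only months 5 and 6 contain both trained and untrained clinics.
- Within clinics, the training indicator has sum of squares 3 × 12 × 0.5 × 0.5 = 9.0. After month effects, 1.143 remains: 1.143 / 9.0 = 12.7%.
- A drift of 0.01 per month shared by all clinics biases the training effect by 0.00. Without month effects the bias is 0.06 (0.01 × 6 months between window midpoints). The Cox model, with no calendar-time term named, is open to a bias of this kind.
- A shift of 0.10 that starts at each clinic's own training passes through in full: 0.10.
- A shift of 0.10 after training in one clinic only passes 0.025-0.0375.

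Section 4.4.1 also describes the pre-training window as the six months before the first CHW training. If that means the first training overall, no month contains both states, 0% of the variance remains, and month effects cannot be separated from training.

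**Step 2. Size in a time-to-event comparison.** Assumptions: two equal groups, exponential times, censoring at 6 months, no frailty, no screening covariates; 50% re-engagement in recently lost patients, so λ = ln 2 / 6 = 0.1155 per month; hazard ratio 0.5 for long-lost patients, so their six-month re-engagement is 1 − 0.5^0.5 = 29.3%. With long-lost share p_k in group k (0 before, 1 after):

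S_k(t) = (1 − p_k) exp(−λt) + p_k exp(−0.5λt), and f_k(t) = −S_k′(t).

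The unadjusted Cox limit is the θ that solves

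∫₀⁶ { f₁ − (f₀ + f₁) θS₁ / (S₀ + θS₁) } dt = 0.

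The before group has p₀ = 0.40 and re-engagement 0.60 × 0.50 + 0.40 × 0.293 = 41.7%. With no training effect:

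| Long-lost share after | Re-engagement after | Apparent HR |
|---|---|---|
| 45% | 40.7% | 0.967 |
| 55% | 38.6% | 0.904 |
| 35% | 42.8% | 1.033 |
| 30% | 43.8% | 1.067 |

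The HR adjusted for the long-lost factor is 1.00 in every row. At 55% the crude rate ratio is 38.6 / 41.7 = 0.93. A true HR of 1.30 would appear as 1.17 at a share of 55% and as 1.38 at 30%. With a weaker prognostic factor (HR 0.7) and a share of 55%, the null HR is 0.948.

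**Step 3. Size for a crude rate, with a strength from the documents.** Section 2.1 cites 42% lower odds of HIV treatment adherence with depressive symptoms. Use odds ratio 0.58 as a stand-in for re-engagement (an assumption), with the factor in 50% of patients before training. If re-engagement without the factor is 50%, then with it the rate is 0.58 / 1.58 = 36.7%. Before training: 0.5 × 0.50 + 0.5 × 0.367 = 43.4%. With a 40% share after training: 0.6 × 0.50 + 0.4 × 0.367 = 44.7%, ratio 1.03. Over base rates of 30-70%, the null rate ratio is 1.02-1.04 for a fall to 40%, 1.04-1.08 for a fall to 30%, and 0.96-0.98 for a rise to 60%.

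**The case against.** The strongest reply has four parts.

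- **The Cox model does adjust for case mix.** A reader might infer that neither model uses anything known at assignment. The documents do not support that: depression, alcohol and drug screening results are prognostic patient characteristics, and their timing is simply not stated. This stands. What remains is that no covariate is documented as fixed at assignment. Screening results are also absent both from the listed database contents and from the data staff will view.
- **The Poisson time effect removes shared drift.** A reader might infer that clearing a backlog of long-lost patients would bias the rate comparison. If the drift is common to all clinics and the windows are group-specific, it does not (bias 0.00 in Step 1). This stands for the Poisson model only, and the support is thin: two months of overlap across about three clusters.
- **No steering of patients is shown.** A reader might infer that supervisors send harder cases to trained CHWs. No section describes how patients are allocated, enrolled CHWs in a cluster train together, and Section 3.2.2 says randomisation will not affect other TB/HIV clinic services. This stands: the bias is possible, not demonstrated. Nor are the two lists wholly different people, since nothing bars a patient from being on both.
- **The illustration is not the planned model, and full stratification would be sparse.** Step 2 omits frailty and screening, and all its inputs are assumed. Crossing 60 CHWs × 2 periods × 3 TB/HIV types × 2 time bands gives 720 cells, with no patient count to show they would be filled. Both points stand, and the fix below uses coarser adjustment.

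**Conclusion.** The concern holds in a limited form. The two patient lists are separate and non-randomised. The Poisson model has no case-mix term. The Cox model relies on post-assignment contact and on screening of unstated timing, without calendar time. A case-mix change that starts at each clinic's own training can be read as a training effect in either model. The Poisson time effect removes only drift shared by all clinics, and only if the pre-training window is group-specific.

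Under the Step 2 assumptions, shifts of 5 to 15 points upwards or 5 to 10 points downwards in the long-lost share give null hazard ratios of 0.97-0.90 or 1.03-1.07. That is modest for a small shift, but enough at the larger end to hide part of a moderate effect or add to it. The direction and size of any real shift are unknown. For a secondary, preliminary outcome in a pilot this is a change the plan should make; it does not undermine the primary stigma analysis.

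**What to change.** In Section 4.4.1:

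1. **Cox model.** Add time since last TB/HIV treatment visit at the patient's start date (the same time zero the model uses), TB only / HIV only / both, and a fixed calendar-time effect.
2. **Poisson model.** Use the number of assigned patients as an offset, and adjust for the same two factors through a few coarse strata or through proportions per CHW and period.
3. **Definitions.** State when screening occurs and where the result comes from. Give one definition of the pre-training window, since Sections 3.5.2g and 4.4.1 can be read differently.
4. **Reporting.** Tabulate case mix before and after training.

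Cost: a few extra parameters; two derived variables, of which time since last visit can come from attendance dates already extracted if the look-back is long enough; and a recorded start date per patient, which the Cox model needs anyway. A minor ethics amendment may be needed if TB/HIV type is taken from the status field, because Section 3.5.2g limits what staff view and rests the absence of patient consent on aggregate, de-identified data. Adjustment removes only measured imbalance.

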2.3 Adapting Training for the Stepped-Wedge Pilot Trial

Based on the findings of the initial training, we will adapt the training for a larger pilot test. We will use a randomized, hybrid Type 2 effectiveness-implementation design¹ to compare the adapted CHW training to usual CHW training (treatment as usual; TAU) in this setting. This type of design builds evidence for the effectiveness of an intervention in a real-world context, while also supporting the transition to implementation for subsequent, larger trials, with an equal emphasis on effectiveness and implementation.

This hybrid Type 2 effectiveness-implementation study will utilize a stepped wedge design to maximize power and ethically ensure that all clinics receive the CHW training, while also including a rigorous comparison condition. In this pilot trial, all clinics will receive the CHW training; each clinic will be randomized to the timing in which their CHWs receive the training.

Before CHWs receive this adapted training, they will receive TAU. In TAU, a CHW is typically deployed to a patient's home who has TB/HIV and has been LTFU for TB and/or HIV treatment with the central goal for supporting re-engagement in TB/HIV care. The CHW Typically goes to the patient's home twice per week for one month, or until the patient has re-engaged in care (if less than one month). CHWs typically meet with supervisors weekly for monitoring, which is limited to target review and does not include additional skills training or psychosocial debriefing. CHWs typically routinely document their visits to facilitate supervision and monitoring, and as part of efforts to roll out screening for depression and SU.

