3.2.2 Stepped-Wedge Trial

We will use a stepped-wedge design.

CHWs will be clustered based on the site at which they work. When recruiting participants, we will aim to recruit approximately 20 CHWs per cluster.

CHWs across all clusters will be recruited and complete a baseline assessment at approximately the same time. In stepped-wedge trials, all groups have different intervals of a baseline period in which they are not exposed to an intervention (which we refer to as “treatment as usual” or “TAU”). Following this, at measurable intervals (steps), one group at a time will receive the training intervention. This process continues until all clusters have received the intervention. Then, at least one more follow-up assessment occurs after all clusters have received the intervention.

In this study, when a cluster receives the intervention (versus continues TAU) depends on whether they are randomized to Training Time #1, Training Time #2, or Training Time #3. Each training time will occur at a measurable intervention (compared to when the baseline assessment was conducted) so that the doses of TAU are discernable.

During data analysis, outcome variables will be compared between people before taking the intervention (TAU only; timepoints are baseline assessment (t1) and pre-training assessment (t2)) and with the same group of people after the intervention (TAU+Training; additional timepoints are 3-month follow-up (t3) and 6-month follow-up (t4) after adjusting for individual random effect and time effect.

Randomization will not affect any other TB/HIV-related clinic services or mental health training.

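### No calendar-time adjustment is stated for the Cox model of time to re-engagement, so fitted as listed its training hazard ratio is a within-clinic before-after contrast

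*Combined protocol and SAP*

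**What the plan says.** Section 4.4.1 of the combined protocol and SAP has two models for re-engagement. Both serve a comparison of patients "in the six months prior to the CHW training compared to six-months following the CHW training".

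- **Poisson model (CHW-level rate):** "accounting for both clinic random effect and the fixed effect of time in the stepped wedge design".
- **Cox model (patient-level time):** "we will use a Cox Proportional Hazard survival model to model the patient-level outcome of time of re-engagement". The clustering term is "A frailty model includes the random effect of clinics to account for unobserved heterogeneity". For covariates the plan says "We will control for amount of CHW contact with the patient" and adds the patient's screening results. An accelerated failure time model replaces it if proportional hazards fails. No calendar time, period or step is named for either survival model.

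The primary model for the Social Distance Scale (4.3.1) also includes "fixed effects of time and the effect of the training". Section 3.2.2 says that outcomes are compared "after adjusting for individual random effect and time effect", and ties this to the CHW assessments t1 to t4.

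The pre-training window is described in two ways. The chart-extraction text in 3.5.2g takes the six months before each group's own training. Section 4.4.1, describing the rates, takes the six months before the first CHW training, which can be read as one common window for all clinics.

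**The concern.** Training is staggered so that its effect can be separated from calendar change. A Cox model does not do this by default, because its time axis is time since the patient was assigned, not the date. Each clinic supplies about six months of untrained patients and then about six months of trained patients. With a clinic effect and no date in the model, the training coefficient takes up whatever else changed between those windows.

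Such change is plausible here. Section 2.3 describes CHW documentation "as part of efforts to roll out screening for depression and SU", and several sections plan around COVID-19. If re-engagement was improving or worsening anyway, the trial could report a training effect on time to re-engagement that training did not cause. The Cox and Poisson results for one outcome would also rest on different adjustments, with nothing to tell the reader so.

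**Working it through.** The plan gives no sample size, event count, hazard ratio or power for this analysis, so there is no stated figure to reproduce.

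**Inputs from the documents.** Three groups of about 20 CHWs (3.2.2); training in months 5, 6 and 7 (section 7); six-month windows before and after training (4.4.1).

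**Assumptions.** Log-hazard drift g per calendar month of 0 to 0.05; 10 patients per CHW per window; baseline hazard 0.15 per month; clinic log-hazard SD 0.2; follow-up ending with the window; true training hazard ratio 1. Clinic was fitted as fixed indicators in place of the frailty. The contact and screening covariates were left out.

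**1. Closed form.** With group-specific windows, the window centres are six months apart in every clinic, so without a date term the false hazard ratio is exp(6g):
- g = 0.01: exp(0.06) = 1.06
- g = 0.02: exp(0.12) = 1.13
- g = 0.03: exp(0.18) = 1.20
- g = 0.05: exp(0.30) = 1.35

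**2. Simulation (300 runs per setting, group-specific windows).** Each cell gives the estimated hazard ratio and the two-sided 5% rejection rate.

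| g | No date term | Linear month | Categorical month |
|---|---|---|---|
| 0 | 1.00, 4% | 1.00, 3% | 1.00, 4% |
| 0.01 | 1.05, 10% | 0.99, 5% | 0.98, 6% |
| 0.02 | 1.13, 25% | 1.01, 5% | 1.03, 6% |
| 0.05 | 1.36, 93% | 1.02, 4% | 0.99, 4% |

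With a common pre-window and no date term, the estimates at g = 0.01, 0.02 and 0.05 are 1.08, 1.14 and 1.41. The before-after problem is present under either window.

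**3. Can calendar month be fitted?** The design has 17 columns: training, two clinic contrasts and 14 calendar months.
- *Group-specific windows:* in month 5, group 1 is trained and groups 2 and 3 are not; in month 6, only group 3 is untrained. The rank is 17 of 17, so the training effect is estimable, but its concurrent information comes from those two months.
- *Common pre-window:* every untrained patient is assigned before month 5 and every trained patient from month 5 on. The training indicator equals the sum of the later month indicators, and the rank is 16 of 17. Categorical month cannot be fitted, and a linear term separates training only by extrapolating the trend.

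**4. Is a linear term enough?** Assumed non-linear changes were projected on training, clinic and linear month, with a true hazard ratio of 1.
- A 20% step at month 6 (group-specific windows): 1.18 without the term, 1.12 with it.
- A 12-month cycle of log-hazard amplitude 0.2 at its worst phase (group-specific windows): 1.26 with or without it.
- A 20% step at month 5 (common window): 1.20 even with it.

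**5. Precision.** At g = 0 with group-specific windows, the standard error of the log hazard ratio is 0.099 without a date term, 0.249 with linear month and 0.388 with categorical month. The ratios are 0.249/0.099 = 2.5 and 0.388/0.099 = 3.9. Across the follow-up assumptions tried, the linear ratio ranges from about 2.0 (full six months) to 2.6 (window-limited). The categorical ratio is about 2.8 or more.

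For a true hazard ratio of 1.3, ln 1.3 = 0.262. Approximate power from these three standard errors is Φ(0.262/0.099 − 1.96) = 75%, Φ(0.262/0.249 − 1.96) = 18% and Φ(0.262/0.388 − 1.96) = 10%. The 75% is a valid figure only if there is no drift.

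**The case against.** The strongest reply is that the Cox paragraph is not a full list of terms. It does not name the training indicator either, it follows directly on a model with a stated time effect, and 3.2.2 speaks generally of a time effect. A reader might infer that the plan deliberately excludes calendar time and discards the randomised timing. The documents do not show that; they show an incomplete specification. But 3.2.2 does not fill the gap. Its adjustment is defined for CHW assessments that chart-extracted patients do not have, and it pairs the time effect with an individual random effect that the Cox model lacks. An analyst following 4.4.1 would have no instruction to add the date.

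A reader might also infer that all secular change is credited to training. Only drift between the two windows is, and the contact and screening covariates may absorb part of it. The simulation omits those covariates, so its figures are for drift that does not act through them. It also has no CHW-level or clinic-by-period variation, so its rejection rates with a date term are a best case.

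Nor does the Poisson model's stated time effect make that model safe. With a common pre-window it meets the same limit.

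Finally, this is a secondary outcome in a pilot, and the adjustment costs much precision. That stands. It is a reason to report the result as imprecise, not to prefer a narrower interval that holds only if nothing else changed.

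**Conclusion.** The concern holds as a gap in specification that has a consequence. Section 4.4.1 states time adjustment for the Poisson model and none for the Cox model or its fallback. Fitted with the listed terms, the training hazard ratio is a within-clinic before-after contrast. Under log-linear drift of 1 to 5% per month and group-specific windows, a null effect would appear as a hazard ratio of about 1.06 to 1.35. The drift, caseload and event rate are assumptions; the documents give none of them. The direction of the bias follows the direction of the drift.

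Whether the adjustment can recover a controlled comparison depends on which pre-training window applies, and 3.5.2g and 4.4.1 leave that unsettled. The primary stigma analysis is not affected by this point.

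**What to change.** 1. **Settle the window first.** Make 3.5.2g and 4.4.1 agree on whether the pre-training window ends at each group's own training or at the first training overall. In the same edit, correct the post-training extraction text in 3.5.2g, which describes its period as the six months before training.
2. **Add the term.** In 4.4.1, give the Cox and accelerated failure time models a fixed effect of calendar time of assignment to the CHW, alongside the training indicator and clinic frailty. State that the training effect is read from that model.
3. **If windows are group-specific,** use categorical month as the main adjustment and a linear month term as a sensitivity analysis, because the linear term removes only linear drift.
4. **If the pre-window is common,** say that categorical month cannot be fitted and that a linear term relies on extrapolation. Label the result an uncontrolled before-after comparison, and state the same limit for the Poisson model.

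No new data are needed, because the assignment date is the natural origin for time to re-engagement. The wording is short once the window is settled. The cost is the loss of precision shown above, so the plan should say in advance that this secondary result will be imprecise and will be reported as such.
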